## **9.2 Procedures in Case of Pregnancy**

If a female study patient becomes pregnant, or plans to become pregnant, during the course of the study, the patient must inform the Investigator, and deferiprone must be stopped and the patient will be immediately withdrawn from the clinical trial. The Investigator must report all pregnancies that occur during the study and within 30 days

after the last dose of study medication, using the Pregnancy Reporting Form and information collected in eCRF. The patient will be followed up and the pregnancy outcome will be reported. Pregnancy outcomes include live birth, spontaneous abortions (loss of pregnancy before 20 weeks of gestation), elective termination, and fetal death/still births (loss of pregnancy after 20 weeks of gestation). Within any of these categories, the fetus or infant must be evaluated for the presence of any congenital anomalies. Any maternal/fetal complications should be also reported. If possible, the health of the child will be followed for 1 year.

The same pregnancy and post-gestation monitoring procedures will also apply in the case where a male patient reports that his female partner has become pregnant. In this case, however, there will be no requirement for the patient to withdraw from the trial.

## **10 STUDY COMMITTEE**

### **10.1 Data Safety Monitoring Board**

An independent Data Safety Monitoring Board (DSMB) will be established to monitor the safety of patients during the course of the study. The DSMB will be responsible for overseeing the conduct of the trial, and will be empowered to recommend stopping the trial if in their judgement continuation is not ethically acceptable on the grounds of safety.

The operating model and the frequency of the interim safety review meetings will be laid out in the DSMB charter. The DSMB will be constituted prior to the enrolment of any patients into the study. The DSMB will be notified of any changes to the protocol or the study conduct. All DSMB meeting minutes and board composition will be submitted to the regulatory authorities with the final clinical study report.

## **11 DATA HANDLING AND STATISTICAL ANALYSIS**

### **11.1 Data Collection and Handling Procedures**

#### **11.1.1 Documentation of Data**

All data obtained during this study are raw data and will be entered promptly by the Investigator or delegate in the source document. eCRF entries are derived from source documents. An explanation must be documented for any missing data. The Investigator will be required to place all source documents in the patients' medical record files. Details of the eCRF completion will be explained to the Investigator.

#### **11.1.2 Corrections to Study Documentation**

Any errors in the study documentation must be crossed out with a single line, leaving the original entry legible. The correction must then be dated and initialled. Incorrect entries must not be covered with correcting fluid, obliterated, or made illegible in any way.

### **11.1.3 Data Processing**

During the study, the study statistician will have read-only access to the data for program development. Integrity of the database will be assured by limiting access through passwords and account control and through regular, secure backups of both the clinical data management files and SAS-related files.

### **11.1.4 Coding**

The following coding dictionaries will be used:

Diseases: Medical Dictionary for Regulatory Activities (MedDRA)

Adverse events: MedDRA

Drugs: World Health Organization (WHO) Drug Dictionary

### **11.1.5 Data Handling**

Discrepancies will be reviewed and resolved online by the clinical study site users or reviewed off-line by Clinical Data Management, the CRO and/or Clinical Research and sent to the study site. A Patient Data Report (PDR) is a generated compilation of data from the database that is presented in a PDF document. The PDR originates from the same HTML files as the eCRFs and can either be generated with no data, with patient and eCRF information (such as patient ID number #, site name, etc.), and/or with all collected response data. A copy of the final PDRs will be sent to the clinical study site after database freeze.

### **11.1.6 Missing, Unused and Spurious Data**

All missing data will be subject to data queries as specified above. All eCRF data will be entered into the electronic database and will be considered for analysis as specified in the statistical analysis plan.

## **11.2 Statistical Analysis**

### **11.2.1 Primary Efficacy Endpoint**

The change from baseline to Week 52 in liver iron concentration (measured by MRI).

### **11.2.2 Secondary Efficacy Endpoints**

- Change from baseline to Week 52 in patient-reported quality of life (SF-36 or Child Health Questionnaire);
- Change from baseline to Week 52 in cardiac MRI T2\*;
- Change from baseline to Week 52 in serum ferritin.

### 11.2.3 Safety Endpoints

- Frequency, severity and time to onset/duration of adverse events (AEs);
- Frequency of serious adverse events (SAEs);
- Discontinuation due to AEs;
- Hematology assessments including hemoglobin, total WBC, ANC and platelets;
- Blood serum clinical biochemistry assessments;
- 12-lead ECG.

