#### 8.2.4.3 Procedures for Adverse/Medical Event Monitoring and Recording

MEs will be collected from the time the ICF is signed, and AEs will be collected from the time the treatment starts. The AEs and SAEs related to the underlying condition will be recorded separately.

Patients will be instructed to report AEs/MEs to the Investigator. Reports of adverse events will be elicited using a verbal probe and recorded in the source documentation and on the Adverse Event page of the eCRF. The Investigator or delegate should always ask the same open-ended and non-leading verbal questions of the patient to inquire about AE/ME occurrence. Appropriate questions include:

“How are you feeling?” or “How do you feel?” or for pediatric patients, “How does your child seem to feel?”

“Have you had any (other) medical problems since your last visit/assessment?” or “Have you felt any different in any way since starting the new medication/treatment or since your last visit/assessment?” or for pediatric patients, “Has your child had any (other) medical problem or seemed to act differently in any way since his/her last visit/assessment?”

“Have you taken any new medicines, other than those provided in this study, since your last visit/assessment?” or for pediatric patients, “Has your child needed to take any medicines, other than those provided in this study, since his/her last visit/assessment?”

Based on the patient’s response to these questions, the Investigator should ask additional questions relevant to the specific complaint, such as:

- How severe is/was the symptom?
- How often did the symptom occur?
- How long did the symptom last?

All AEs/MEs will be recorded and evaluated by the Investigator for their seriousness, severity, and relationship to the investigational product or study.

The Investigator should attempt to establish a diagnosis of the AE based on signs, symptoms, and/or other clinical information. Wherever possible, a diagnosis should be documented rather than the individual signs/symptoms.

The Investigator must also question the patient about any previously reported AEs that have not resolved.

The Investigator will then rate the intensity, seriousness, and causality of the AEs and will also document any measures taken to address the AE. Causality should be rated in terms of relationship to the study medication as follows: not related, possibly related, probably related, definitely related. See [Section 8.2.4.4](#) for further definitions of

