#### 8.2.4.9 Adverse Event of Special Interest – Neutropenia (Definitions and Management)

##### **Definitions**

*Mild Neutropenia:* A confirmed ANC  $\geq 1.0 \times 10^9/L$  and  $< 1.5 \times 10^9/L$ .

*Moderate Neutropenia:* A confirmed ANC  $\geq 0.5 \times 10^9/L$  and  $< 1.0 \times 10^9/L$ .

*Severe Neutropenia/Agranulocytosis:* A confirmed ANC  $< 0.5 \times 10^9/L$ .

An absolute neutrophil count (ANC) is confirmed as being less than a specified value if two consecutive counts (maximum 3 days apart) are both less than the specified value. If both consecutive counts are below  $1.5 \times 10^9/L$  but not in the same severity category of neutropenia, a third count will be required to determine the severity.

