##### **Management**

*Mild Neutropenia* (two consecutive Absolute Neutrophil Counts  $\geq 1.0 \times 10^9/L$  and  $< 1.5 \times 10^9/L$ ):

Patients receiving deferiprone treatment who experience mild neutropenia (ANC  $\geq 1.0 \times 10^9/L$  and  $< 1.5 \times 10^9/L$ ) should continue treatment. The patient's ANC will be monitored every 2 days until resolution of the event, defined as two consecutive ANC  $\geq 1.5 \times 10^9/L$ . If the ANC remains  $\geq 1.0 \times 10^9/L$  and  $< 1.5 \times 10^9/L$  by the end of a two-week period (14 days):

- The patient will be withdrawn from the study and monitored until resolution of the event.
- The patient will be advised regarding protective isolation.
- The Investigator will notify ApoPharma Inc. by fax.
- The Investigator will examine patient the same day (if possible) including drug history and physical examination.

However, if the patient has a mild neutropenia and develops an infection, therapy must be interrupted immediately and neutrophil count must be obtained and monitored more frequently (every 2 days if ANC  $< 1.5 \times 10^9/L$ ) until resolution of the event, defined as two consecutive ANC  $\geq 1.5 \times 10^9/L$ . Patients should be advised to report immediately to their physician any symptoms indicative of infection such as fever, sore throat, and flu-like symptoms. In presence of confirmed fever and/or infection, they will be required to have their neutrophil counts tested as soon as possible and no later than 24 hours after the symptoms of infection are detected. Patients will be provided with an emergency services card with contact information, and the patient/legal guardian will be advised to carry this card at all times. Therapy with deferiprone can be initiated once all symptoms have been resolved and it is deemed safe by the Investigator.

Moderate Neutropenia (two consecutive Absolute Neutrophil Counts  $\geq 0.5 \times 10^9/L$  and  $< 1.0 \times 10^9/L$ ):

Patients receiving deferiprone treatment who experience moderate neutropenia (ANC  $\geq 0.5 \times 10^9/L$  and  $< 1.0 \times 10^9/L$ ) will immediately interrupt treatment, and the patient's ANC will be monitored every 2 days until resolution of the event, defined as two consecutive ANC  $\geq 1.5 \times 10^9/L$ . If the ANC remains  $< 1.5 \times 10^9/L$  by the end of a two-week period (14 days):

- The patient will be withdrawn from the study and monitored until resolution of the event.

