- Provide protective isolation; if clinically indicated, admit patient to hospital and obtain q4h vital signs.
- The Investigator will notify ApoPharma Inc. by fax.
- The Investigator will examine the patient the same day, if possible, including drug history and physical examination.
- If possible, obtain viral studies (CMV, parvovirus, hepatitis A/B/C), serum ALT, BUN, creatinine, and 10 mL serum split into two 5-mL aliquots for frozen storage, for future analysis.

Severe Neutropenia/Agranulocytosis (two consecutive Absolute Neutrophil Counts  $< 0.5 \times 10^9/L$ ):

Patients receiving deferiprone and who experience severe neutropenia/agranulocytosis (ANC  $< 0.5 \times 10^9/L$ ) will immediately discontinue treatment. The patients will be withdrawn from the study and will be followed daily until two successive ANCs are  $\geq 1.5 \times 10^9/L$ :

- The patient will be withdrawn from the study and monitored until resolution of the event.
- Provide protective isolation; if clinically indicated, admit patient to hospital and obtain q4h vital signs.
- The Investigator will notify ApoPharma Inc. by fax.
- The Investigator will examine the patient the same day, if possible, including drug history and physical examination.
- If possible, obtain viral studies (CMV, parvovirus, hepatitis A/B/C), serum ALT, BUN, creatinine, and 10 mL serum split into two 5-mL aliquots for frozen storage.
- Collect a blood sample to attempt to identify genetic or other biomarkers related to agranulocytosis (optional).
- If possible, obtain bone marrow aspirate for:
  - Histology
  - Progenitor culture
  - Frozen storage (1 mL sample)
- If possible, obtain bone marrow biopsy (minimum length 3 mm).
- Perform septic work-up including chest X-ray, blood, urine and throat cultures.
- Obtain q4h temperatures from patient (monitored by family at home if patient is not in the hospital).
- If warranted, administer granulocyte stimulating factors, such as G-CSF 10 µg/kg, as an inpatient if possible, beginning the same day that the ANC is confirmed as  $< 0.5 \times 10^9/L$ ; administer daily until ANC is  $> 1.5 \times 10^9/L$  on two consecutive days.
- If ANC  $< 0.5 \times 10^9/L$  for 7 days, repeat bone marrow biopsy and aspirate weekly during the period of agranulocytosis, if warranted.

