8.5 Biochemistry, Hematology and Urinalysis

All analyses of laboratory data will be based on the planned visits. Laboratory data collected at unscheduled visits will be available in the data listings but not included in summary tables.

Descriptive statistics for each clinical laboratory test will be presented for each scheduled visit. Change from baseline to each follow-up assessment will be also presented. According to the laboratory normal ranges, laboratory test results will be categorized as low (< lower normal limit), normal (within normal range), and high (> upper normal limit). Shift tables comparing the distributions of these three categories at baseline versus end of treatment will be presented.

Urinalysis assessments will consist of pH, specific gravity, ketones, blood, glucose, and protein. The raw data listings for each individual patient will be produced for further evaluation, whenever needed.

Clinically significant laboratory values will be reported as AEs.

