14.3 Safety

14.3.1 Hematology

Figure 14.3.1.1 Mean line graph for hemoglobin over visit

Figure 14.3.1.2 Proportion of patients with abnormal hemoglobin at each assessment

Note: Similar graphs will be produced for total white blood cell (WBC), absolute neutrophil count (ANC), and platelets.

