Serum ferritin (µg/L)	Month 3	xx.x ± xx.x	xx.x ± xx.x	xx.x ± xx.x	(xx.x, xx.x)
	Month 6	xx.x ± xx.x	xx.x ± xx.x	xx.x ± xx.x	(xx.x, xx.x)
	Month 9	xx.x ± xx.x	xx.x ± xx.x	xx.x ± xx.x	(xx.x, xx.x)
	Month 12	xx.x ± xx.x	xx.x ± xx.x	xx.x ± xx.x	(xx.x, xx.x)

Data source: 16.2.21 Listing of serum ferritin

Table 14.2.3.4 Trend analysis for serum ferritin over time

	Deferiprone	Deferoxamine	Deferiprone minus Deferoxamine	P-value
Slope: Mean ± SE	xx.x ± xx.x	xx.x ± xx.x	xx. x ± xx.x	0.xxxx

Data source: 16.2.21 Listing of serum ferritin

Table 14.3.1.1 Overall summary of adverse events

	Treatment		
	Deferiprone	Deferoxamine	
N	xxx	xxx	P-value
Number of patients experiencing at least one AE	xx (xx%)	xx (xx%)	0xxxx
Number of patients experiencing at least one severe AE	xx (xx%)	xx (xx%)	0xxxx
Number of patients experiencing at least one serious AE	xx (xx%)	xx (xx%)	0xxxx
Number of patients experiencing at least one related* AE	xx (xx%)	xx (xx%)	0xxxx
Number of patient deaths	xx (xx%)	xx (xx%)	0xxxx
Number of patient withdrawals due to AEs	xx (xx%)	xx (xx%)	0xxxx

*Includes possibly, probably, and definitely related. Worst case scenario of causality between the investigator and company's assessment.

Data source: 16.2.28 Listing of adverse events

Table14.3.1.2 Adverse events

		Treatment		
		Deferiprone (N=xxx)	Deferoxamine (N=xxx)	
Exposure (patient-years): x.xx		Exposure (patient-years):x.xx		
Total Events: xxx		Total Events: xxx		
System Organ Class Preferred Term	n Patients (%)	n Patients (%)		P-value (Fisher's exact test)
CCCCCCC	x (x.x)	x (x.x)		0xxxx
Ccccccc	x (x.x)	x (x.x)		0xxxx
Cccccc	x (x.x)	x (x.x)		0xxxx
Ccccccc	x (x.x)	x (x.x)		0xxxx
.....

Note: Similar tables will be produced from Table 14.3.1.3 to Table 14.3.1.7

Data source: 16.2.28 Listing of adverse events

Table 14.3.1.8 Adverse events by causality

		Treatment	
		Deferiprone (N=xxx)	Deferoxamine (N=xxx)
System Organ Class Preferred Term	Relatedness (worst case)	Patients reporting (n=xx)	Patients reporting (n=xx)
CCCCCCCC		x (x.x)	x (x.x)
cccccc	Not Related	x (x.x)	x (x.x)
	Related*	x (x.x)	x (x.x)
cccccc	Not Related	x (x.x)	x (x.x)
	Related*	x (x.x)	x (x.x)
.....

*Possibly, Probably, or Definitely Related

Data source: 16.2.28 Listing of adverse events

Table 14.3.2.1 Temperature at each assessment

	Treatment				
	Deferiprone		Deferoxamine		
Visit	N	Mean ± SD (Min, Max)	N	Mean ± SD (Min, Max)	P-value (T-test)
Baseline	xxx	xx.x ± xx.x (xx, xx)	xxx	xx.x ± xx.x (xx, xx)	0.xxxx

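### Neutropenia at the protocol's own ANC cut-offs has no laboratory-based patient count by arm, while the planned AE comparison is exposed to closer mandated counting on deferiprone

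*Protocol*

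**What the plan says.** Protocol 11.2.3 lists "Frequency, severity and time to onset/duration of adverse events (AEs" as a safety endpoint, and hematology including ANC as another. Protocol 8.2.4.9 makes neutropenia the event of special interest: mild, moderate and severe correspond to a confirmed ANC below 1.5, 1.0 and 0.5 × 10⁹/L. A count is confirmed as low "if two consecutive counts (maximum 3 days apart) are both less than the specified value". That rule names no arm, and neither does the requirement for a third count when the first two fall in different grades.

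The management text in the same section does name an arm. "Patients receiving deferiprone treatment who experience mild neutropenia" have their ANC repeated every 2 days, as do those with moderate neutropenia. "Patients receiving deferiprone and who experience severe neutropenia/agranulocytosis" are followed daily. Protocol 4.6 likewise words the rule for moderate neutropenia for deferiprone. Routine hematology is the same in both arms: weekly to Week 26, then biweekly, each ± 3 days (Protocol 5.4). These counts may be done at local laboratories (Protocol 8.2.2).

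On recording, Protocol 8.2.4.3 says "Wherever possible, a diagnosis should be documented rather than the individual signs/symptoms".

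In the SAP, the shell for Table 14.3.1.2 compares each AE term between arms under the column "P-value (Fisher's exact test". For ANC there are weekly value and change tables, shift tables to the last assessment, and a figure of the proportion abnormal at each assessment ("Similar graphs will be produced for total white blood cell (WBC), absolute neutrophil count (ANC), and platelets"). SAP 8.5 adds: "Laboratory data collected at unscheduled visits will be available in the data listings but not included in summary tables".

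**The concern.** Agranulocytosis is the most significant serious risk that Protocol 1.2 attributes to deferiprone, so a reader of the report will look first for how many patients in each arm had neutropenia at each grade. The planned outputs answer this only through AE terms. Those terms may be recorded more completely on deferiprone, where a low count triggers mandated repeats, than on deferoxamine, where a repeat is left to the site. The report would then show a between-arm p-value with no patient-level laboratory count at the same cut-offs to set beside it. At stake is the interpretation of the main safety comparison, not the non-inferiority result and not patient protection.

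**Working it through.** **The plan's own safety figure.** SAP 3.2 gives the chance of at least one event among 213 patients as 98% at a 2% rate and 88% at a 1% rate. With 1 − (1 − p)ⁿ: 1 − 0.98²¹³ = 0.9865 and 1 − 0.99²¹³ = 0.8824. Both agree within rounding. This figure concerns seeing any event; it does not bear on comparing arms.

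**What each planned ANC output can show**

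| Output | Basis | Counts patients ever below 1.5 / 1.0 / 0.5? |
|---|---|---|
| Tables 14.3.6.1.1–2, ANC version | N, mean, SD, minimum, maximum per week, by arm | No. The minimum shows that someone was low, not how many |
| Figure 14.3.1.2, ANC version | Proportion abnormal at each assessment; SAP 8.5 defines categories by laboratory range, both low and high | No. Per visit, and other cut-offs |
| Tables 14.3.6.1.3–4, ANC version | Low/normal/high at baseline versus last assessment | No. A patient who has recovered can appear normal |
| AE tables | Recorded terms, Fisher's test | Only as recorded by the investigator |

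**Can routine counts confirm neutropenia without an extra visit?** Let the two visit-day offsets a and b each lie between −3 and +3.
- Weekly: the interval is 7 + (b − a), from 1 to 13 days. If offsets are independent and uniform (assumption), it is 3 days or less in 3 + 2 + 1 = 6 of 49 pairs, or 12%.
- Biweekly: the interval is 14 + (b − a), from 8 to 20 days, and never 3 days or less.
- The 12% is per pair, not per patient. With 3, 4 or 5 consecutive low weekly counts, the chance that some adjacent pair qualifies is 24%, 35% or 44%.

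On deferoxamine, confirmation under the protocol definition therefore depends largely on the site ordering an extra count.

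**What unequal recording could do to the Fisher comparison.** Inputs: 142 and 71 patients (SAP 3.2); rates of 6.2% for neutropenia and 1.7% for agranulocytosis in deferiprone trials (Protocol 1.2); 3% as an intermediate assumption. The documents give no deferoxamine rate, so each rate is assumed equal in both arms. Recording on deferiprone is taken as complete. The share of deferoxamine cases recorded is not given, so the whole range is shown.

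Expected cases at 6.2%: 142 × 0.062 = 8.8 on deferiprone and 71 × 0.062 = 4.4 on deferoxamine. With 50%, 12% or 0% of the latter recorded, 2.2, 0.5 or 0 remain. The table gives the probability that the two-sided Fisher test has p < 0.05 with the higher rate on deferiprone, summed over the exact binomial distributions.

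| Share of deferoxamine cases recorded | True rate 6.2% | 3% | 1.7% |
|---|---|---|---|
| 100% | 1.3% | 0.3% | ≤ 0.1% |
| 50% | 8.5% | 1.0% | ≤ 0.1% |
| 12% | 34% | 2.2% | ≤ 0.1% |
| 0% | 52% | 2.8% | ≤ 0.1% |

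The low-rate columns are small because the smallest significant result against 0 of 71 is 9 of 142 (p = 0.031), while only 142 × 0.03 = 4.3 or 142 × 0.017 = 2.4 deferiprone cases are expected.

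**The case against.** Several counter-arguments are sound and limit the point.

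- A reader might infer that neutropenia reaches the report by arm only through AE terms. That is too strong. ANC values, changes, shifts and proportions abnormal are all planned by arm, and the weekly tables leave out unscheduled repeats, so extra deferiprone counts do not enter them. What is missing is a per-patient count at the protocol cut-offs.
- A reader might infer that a deferoxamine case cannot be recorded without a repeat count. The documents do not support this. Protocol 8.2.2 and 8.2.4.2 and SAP 8.5 have clinically significant laboratory findings recorded as AEs, with no repeat required. Protocol 1.2 lists decreased neutrophil count separately from neutropenia. The confirmation rule names no arm, and the ANC test within 24 hours of fever or infection is worded for patients generally. All this moves the recorded share toward 100%, though it does not make follow-up equal.
- The 34% and 52% are not estimates. They combine a rate taken from deferiprone trials with very low deferoxamine recording, and 0% would mean that no site ever repeated or recorded a low count. The Fisher p-values also drive no decision rule.
- Scheduled counts are not a perfect remedy. Severe or persistent neutropenia on deferiprone leads to withdrawal, which ends scheduled counts there, so a scheduled-only minimum can miss deep nadirs. This stands, and is why the fix needs a second, all-counts panel and a footnote.
- It is tempting to treat the lack of an AE onset/duration table as a serious gap as well. The SAP specifies none, but Protocol 11.4.1.4 specifies none either and commits generally to listings and summary tables, SAP 8 promises descriptive statistics for continuous safety variables, and an AE listing is planned. For AEs other than neutropenia it is a minor omission.

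**Conclusion.** The point holds in limited form. The SAP has no laboratory-based count, by arm, of patients meeting the protocol's neutropenia cut-offs, and its AE comparison is open to unequal follow-up because intensive repeat counts are mandated only on deferiprone. The direction of any resulting bias is against deferiprone; its size cannot be fixed from the documents. Assuming equal true rates and complete recording on deferiprone, the chance of a falsely significant excess runs from 1% to 52% at a 6.2% rate, from 0.3% to 3% at 3%, and is at most about 0.1% at 1.7%, as deferoxamine recording falls from 100% to 0%. The material does not show that the comparison will mislead, only that the planned outputs could not separate a drug effect from closer counting. This is a worthwhile, inexpensive improvement.

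**What to change.** Add to SAP 8.5 a by-arm summary, in the Safety population and separately for SCD and non-SCD patients, of patients whose lowest post-baseline ANC was below 1.5, 1.0 and 0.5 × 10⁹/L, in two panels:

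1. Scheduled counts only, central or local, for comparing the arms.
2. All counts, including unscheduled and local ones, shown descriptively, with episodes confirmed under Protocol 8.2.4.9, their onset day and their duration.

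Footnote that repeat counts were mandated only on deferiprone, and that withdrawal for neutropenia ends scheduled counts, so panel 1 may understate deep nadirs on deferiprone. State how local counts enter: the hematology shells cite listing 16.2.11, while local laboratory results have their own listing, 16.2.31.

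The cost is SAP wording, two small tables, and merging central and local counts already collected. The severe row will be sparse, at about 142 × 0.017 = 2.4 deferiprone patients. SAP 14 leaves room for extra tables, but specifying this one before results are seen avoids a post hoc choice on the drug's main safety risk.
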